10.4.2 Documentation of concomitant medication

Any of the following concomitant medication consumption and dosages will be recorded in the CRF: Antibiotics, diuretics, anti-inflammatory, psychiatric medication, medication used to treat adverse events, cardiac, renal and endocrinology medication and any other medication that might affect urine output.

If there is a medical requirement to change OAB, diuretics or antidepressant medication during the study, these changes will be recorded and the patient will continue the study as planned.

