7.1 ITT population

Treatment of missing values:

- Subjects missing data "not in random" will be imputed as "failure" on dichotomous endpoints.
- "Failures" (not MAR) include:
 - Subject leaves the study due to related AE
 - Device explant
 - o Lack of effect that results in significant increase of UUI medication
 - Need for other 3rd line therapies for the management of UUI

Document ID	Revision / Date	Page
G02-CLP-0009	Rev. 06 / 18 May 2022	11 of 26

- Baseline values will not be imputed
- Missing values in ITT not due to "failure" will be imputed using multiple imputation (MI).

Multiple imputation will be applied to the primary and three secondary endpoints. The 'additional endpoint' analyses will not use multiple imputation. The imputation procedure will be performed on the continuous outcomes (e.g. number of incontinence episodes). Based on the imputed continuous outcome, the response will be defined accordingly for each endpoint.

The hypotheses will be tested by performing the logistic regression on each imputed dataset. Then SAS PROC MIANALYZE procedure will be used to calculate the combined confidence interval and the corresponding p-value. The evaluation on each endpoint will be successful if the lower limit of the confidence interval is above 50%. In addition, the primary analysis will present the observed frequency of responders and descriptive statistics of response rates over all imputed datasets.

Fifty (50) imputed datasets will be created (the seed is set to 123456).

The imputation will be done using covariates: Age, BMI, average number of urgency leaks, average number of urgent voids, HRQL score and OAB duration at baseline. This list might be reduced if the model fails to converge.

Because MI assumes missing at random (MAR), sensitivity analyses (i.e. tipping point) described below, will be conducted to test the effects of other patterns of missingness.

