12.8 Covariate, Subgroup, and 'Poolability' Analyses

Covariate analyses will be done by comparing the primary endpoint by the levels of the covariate at baseline, where continuous variables will be coded into two levels by median split. Analyses will be done by logistic regression. Covariates will include, but are not limited to:

- Age
- BMI
- OAB duration at baseline
- US vs. Outside of US (OUS)
- Race and ethnicity
- Baseline average urgency leaks/day
- Baseline average voids/day
- Smoking history (Past/Current/Never)
- Concomitant OAB medication at time of screening
- Ratio between average stress related leaks and average urgency related leaks at baseline.

For each of the listed above covariates descriptive statistics of the primary endpoint by covariate levels will be

Document ID	Revision / Date	Page
G02-CLP-0009	Rev. 06 / 18 May 2022	23 of 26

presented. Continuous covariates will be divided into quartiles for this presentation. Additionally, formal subgroup analyses will be conducted to assess the effects on the primary endpoint of antidepressant medications and OAB medication, and also to assess the potential impact of COVID-19 on the study outcomes.

The analyses for antidepressant medications and OAB medications will be structurally similar. The first level of the analyses for each medication type will compare treatment effect (success rates) among those taking and not taking the respective medication at baseline. This will be performed as a logistic regression model, with baseline status as an indicator variable. If there is no difference in outcome, the second level of the analysis will be a logistic regression analysis on all subjects, with an indicator variable for changes in medication (lower, same or higher total dosage). If there is a differential effect concerning baseline status, the second level analysis will be comprised of two analyses; one only consisting of the subjects on the respective medication at baseline, with an indicator for any subsequent changes, and this will be repeated for the complementary subgroup of those subjects not on the respective medication at baseline. For each level of analysis, the success rate for each level of the subgroup will be reported for completeness. It should be noted that changes in usage of antidepressants and OAB medications will need to be defined and filtered from the concomitant medications form in exploratory fashion.

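### SAP 12.8 relates 6-month success to later OAB-medication change, although SAP 7.1 treats increases as a result of non-response, so the coefficient cannot be read as a medication effect

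*SAP*

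**What the plan says.** SAP 12.8 states the purpose: "formal subgroup analyses will be conducted to assess the effects on the primary endpoint of antidepressant medications and OAB medication". It works in two levels. Level 1 compares success rates between women taking and not taking the drug class at baseline. If no difference is found, "the second level of the analysis will be a logistic regression analysis on all subjects, with an indicator variable for changes in medication"; this variable separates a fall, no change and a rise in total dose. Where level 1 does show a difference, level 2 is fitted separately in baseline users and non-users, "with an indicator for any subsequent changes". No cut-off date, early-response covariate, test or alpha is given. The change variable is left open: "changes in usage of antidepressants and OAB medications will need to be defined and filtered from the concomitant medications form in exploratory fashion".

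Three other provisions bear on this model.
- SAP 7.1 lists among the failures that are not missing at random: "Lack of effect that results in significant increase of UUI medication". Missing data of that kind "will be imputed as 'failure' on dichotomous endpoints".
- Protocol 10.4.2 keeps women with a medically required change in the study: "If there is a medical requirement to change OAB, diuretics or antidepressant medication during the study, these changes will be recorded". Their own diary then decides the outcome.
- Protocol 10.4 and inclusion criterion 7 ask women on antimuscarinics or beta-3 agonists to agree to stay on stable medication until month 12.

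**The concern.** Level 1 uses a baseline variable and raises no such problem. Level 2 uses something that happens after treatment starts and may be a response to how the woman is doing. The question asked is whether the drug affects success. The model tests whether dose change and success are associated, and they will be associated whenever poor response prompts an increase, even if the drug does nothing.

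SAP 7.1 supplies that mechanism for UUI medication. It also adds some circularity: for a woman whose endpoint is missing because of an increase for lack of effect, the increase is the reason for the failure score, and level 2 would then use the increase to predict that score.

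In a single-arm, open-label trial where each woman is her own control (Protocol 5.2), added OAB medication is an obvious rival explanation for improvement. The bias pushes the *higher* category towards failure. A result in which more drug goes with less success could be taken as reassurance that drugs did not produce the responders, while a real contribution among women who increased and then responded goes unseen.

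**Working it through.** **Inputs from the documents.** Assumed success is 65% against a goal of 50%, with N = 150 and 15% attrition (SAP 9), so about 150 × 0.85 = 127.5, or 128, evaluable women. The one related figure in the plan is the primary sample size of 114. The exact one-sided binomial test at n = 114 needs 68 successes, with alpha 0.0244 and power 0.9015, so 114 reproduces at 90% power. No sample size, alpha or event rate is given for level 2.

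**Assumed.** Two-sided 0.05, and the rates of dose change below.

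**1. Reverse causation, no drug effect.** If increases occur in a fraction u_S of successes and u_F of failures, success among women with an increase is

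0.65·u_S / (0.65·u_S + 0.35·u_F).

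With u_S = 5%, and u_F = 10%, 15% or 20%:
- 0.0325 / (0.0325 + 0.0350) = 48%
- 0.0325 / (0.0325 + 0.0525) = 38%
- 0.0325 / (0.0325 + 0.0700) = 32%

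All are below 65% although the drug does nothing. At n = 128 these settings mean about 83.2 × 0.05 = 4.2 increases among successes, and 44.8 × 0.10 = 4.5, 44.8 × 0.15 = 6.7 or 44.8 × 0.20 = 9.0 among failures.

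Simulated rejection of the lower/same/higher model by likelihood-ratio (LR) test:

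| Increase, failures vs successes | Decrease, failures vs successes | n = 128 | N = 150 |
|---|---|---|---|
| 5% vs 5% (no link) | 5% vs 5% | 8% | 7% |
| 10% vs 5% | 5% vs 5% | 16% | 18% |
| 15% vs 5% | 5% vs 5% | 39% | 44% |
| 20% vs 5% | 5% vs 10% | 69% | 76% |

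With an overall Wald test at N = 150, the last three rows become about 10%, 35% and 68%.

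**2. Scoring rule alone.** Let k women have an increase and all be scored failure, with the rest at 65% success and n = 128. For k = 2 the other 126 split into 82 successes and 44 failures:

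LR = 2[82 ln(82/126) + 44 ln(44/126) − 82 ln(82/128) − 46 ln(46/128)] = 4.15, p = 0.042 (Fisher 0.127).

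For k = 3 (81 and 44), p = 0.013 (Fisher 0.0475). So two or three such women can be enough under an LR test. The choice of test matters: for k = 5 the all-failure cell separates, and the Wald p is about 1.00 while the LR p is 0.0014.

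**3. Masking.** Suppose 65% would respond without added drug, 25% of the other women and 5% of the responders have an increase, and the drug turns 20% of those increased non-responders into successes (n = 128). Then 44.8 × 0.25 = 11.2 increase and 2.24 are rescued. Success is (4.16 + 2.24) / (4.16 + 11.2) = 42% with an increase, against 79.04 / (79.04 + 33.6) = 70% without. The drug helped, yet the contrast points the other way. The LR test significantly shows women with an increase doing worse in 90%, 57%, 36% and 8% of trials at rescue rates of 0%, 20%, 30% and 50%.

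**4. Does adjustment help?** Leak counts were simulated with no drug effect, and with increases in 18% of women below 50% reduction at month 3 against 4% of the others. The unadjusted test rejects in 45% of trials if the decision follows the diary, and in 58% if it follows the underlying response. Adjusting for the month-3 diary brings these to 5.6% and 16%.

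**The case against.** The strongest reply is that this is a supportive analysis with no decision attached. SAP 12.8 reports success rates at every level of each subgroup, SAP 12.5 lists each woman's concomitant medication with dose and dates, and SAP 12.8 calls the definition of change exploratory. A careful reader could bound the drug contribution from those outputs. This lowers the stakes, but the success rates by level are the same confounded contrast, and the listings do not correct it.

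Several stronger readings are tempting, and the documents do not support them.
- *That the test will reject for the wrong reason.* It can. The documents give no rates of change, participants agree to stable OAB medication until month 12, no test is named, and a Wald test may not reject when a cell is all failures.
- *That the same is shown for antidepressants.* SAP 7.1 speaks of UUI medication only. The antidepressant model shares the unadjusted post-baseline structure, but nothing in the documents says poor bladder response leads to antidepressant changes.
- *That every woman with an increase is scored a failure.* The rule applies to missing endpoint data. Protocol 10.8.1 is narrower still: it describes women who leave the study and joins the medication increase to third-line therapy with *and*, where SAP 7.1 lists them separately. Women who stay are scored on their diary.
- *That the primary result is biased by this model.* The test against 50% does not use it.

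**Conclusion.** The point holds for the second-level OAB-medication model, including its versions within baseline users and non-users. The exposure follows baseline, the plan itself describes it as a consequence of non-response, and part of the outcome is scored from it. The coefficient cannot answer the question SAP 12.8 asks. The direction of the bias does not depend on the exact rates: any excess of increases among women who are not responding pulls *higher* towards failure.

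The size does depend on them. With no drug effect, false rejection under an LR test at 0.05 is about 16-76% over the assumed settings, against 7-8% when changes are unrelated to outcome, and it is lower with a Wald test. The masking figures also rest on assumed increase and rescue rates; at 50% rescue the misleading result is uncommon (8%). This is worth correcting because the analysis bears on a main rival explanation for the response. It remains a supportive analysis, and the primary conclusion does not rest on it.

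**What to change.** Revise the level-2 OAB-medication model in SAP 12.8:
1. Count only dose changes that start before the 6-month diary.
2. Fit the model to observed 6-month outcomes. Leave out women whose failure was assigned under SAP 7.1 and report their number separately.
3. Adjust for percent leak reduction at a fixed diary before the change. A month-3 landmark works: count changes from month 3 to month 6 for everyone, with the month-3 diary as covariate. This gives women with no change the same reference visit.
4. Label the analysis descriptive, and state that the unadjusted association is not read as a medication effect.
5. Add a sensitivity analysis of the primary endpoint in which women with an OAB-medication increase before the 6-month diary count as non-responders. This addresses the rival explanation directly, without needing the regression.

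Item 4 also suits the antidepressant model, because it has the same structure.

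The cost is SAP wording, one covariate from a diary already collected, and one extra table. The landmark counts fewer changes, and some women leave this supportive model. Some feedback remains because the 3-day diary is noisy: 16% rejection in the harder setting of step 4. Leaving out assigned failures also selects on outcome, which is why their number must be shown. The primary analysis is untouched.
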